4. CR-HIV (primary outcome) is a couple-level binary indicator of any HIV risk (e.g., yes=1 vs. no=0), which is an algorithm based on whether one or both partners report condomless anal or vaginal sex with a HIV serodiscordant or status-unknown primary or other partner in the past 3 months. Couples are coded as 0 if neither partner reports condomless anal or vaginal sex. If one or both partners in the dyad report condomless sex with a serodiscordant or status-unknown primary or other partner, then the couple is coded as 1 if (i) the HIV-negative participant is not adherent to PrEP and/or (ii) the HIV-positive participant is not virally suppressed. Sexual risk behavior will be measured using the assessment that we have used in our previous studies to explore the number of occasions of different sexual acts (vaginal, anal; receptive, insertive) with three different types of partners (primary partner, casual partner, paying partner), use of condoms during the past 3 months, and knowledge about partners' HIV status. Assessments ascertain sexual behaviors with non-trans male, non-trans female, and transgender partners, and will be asked at each follow-up. At-risk sex will be defined as any vaginal or anal intercourse without condoms that occurs with a person of known positive or unknown serostatus during the follow-up period. Of the participants who report condomless sex with a serodiscordant or unknown serostatus partner, we will attempt to assess PrEP use using dried blood spot (DBS) procedures for biological measurement of adherence from tenofovir diphosphate concentrations in blood plasma. We will use dosing categories for quantification similar to those used in past drug-level studies of PrEP adherence, allowing us to estimate the number of tablets participant are taking per week (e.g., 700-1249 fmol for 4-6x per week and > 1250 for daily dosing). HIV-positive participants will have their blood drawn at each follow-up visit to determine viral suppression. Viral suppression is indicated by an undetectable HIV-1 level on the COBAS® AmpliPrep/COBAS® TaqMan® HIV test kit (Roche Molecular Systems, Inc.), which has a threshold for undetectability = < 20 copies/mL and is conducted at each follow-up assessment visit. Our secondary outcomes include self-report HIV and STI testing over the 12 months of follow-up.

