Auxiliary variables will be included to help meet the MAR assumption;^{88, 89} sensitivity analyses will be conducted with weighted MI to assess the MAR assumption's robustness⁹⁰ using SAS⁹¹ and Mplus.

Primary analyses to address Primary Specific Aim 1. If the CHIP intervention is successful, a lower proportion of intervention participants will engage in CR-HIV relative to control group participants following intervention exposure. Therefore, to address Specific Aim 1 we hypothesize that the odds of CR-HIV will be lower for CHIP participants than for control participants (Hypothesis 1). Our primary interest is to estimate the marginal or population-average effects of CHIP exposure on CR-HIV rather than the effect for a hypothetical average subject or couple.⁹² Moreover, within-subject and within-couple CR-HIV correlations are nuisance parameters rather than quantities of interest to be modeled explicitly. Finally, the statistical literature indicates the superior performance of generalized estimating equations (GEE) relative to generalized linear mixed models (GLMMs) for the analysis of dyadic data with categorical outcomes such as CR-HIV.⁹³ Accordingly, we will use GEE for the proposed primary analysis to test Hypothesis 1 by a planned time-averaged comparison of post-baseline measurements of CR-HIV from the intervention group with the post-baseline measures of CRHIV from the control group. Alpha (α) will be set at .05 for this planned comparison. Any additional post-hoc comparisons (e.g., paired comparisons of groups at each time point) will maintain nominal alpha of .05 through the use of simulation-based stepdown multiple comparison methods.⁹⁴ The alternating logistic regression (ALR) approach implemented in SAS PROC GENMOD will be used to address the 3-level clustering of observations within participants and participants within dyads. Though GEE estimates are consistent even if the correlation structure is misspecified, GEE's statistical efficiency improves as the working correlation structure more closely approximates the actual correlation structure;⁹⁵ therefore, various correlation structures suitable for the study's design will be considered (e.g., exchangeable; nested-1).⁹⁶ The QIC statistic will be used to select the final correlation structure.⁹⁷ Couple serostatus will be included as a covariate as required by the stratified randomized design.⁹⁸ Additional relevant covariates such as relationship length, as well as intersectionality criteria and structural drivers (e.g., age, race/ethnicity, poverty, unemployment) will be included if they improve QIC. We will use Robust Huber-White "sandwich" standard errors to obtain correct inferences even if the chosen correlation structure remains slightly misspecified.

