Secondary exploratory dyadic analyses. Intact dyads enable analyses that explore how predisposing factors, such as relationship functioning and gender minority stressors affect behavior change in partnerships. We will extend the analyses described above to include actor and partner effects for covariates and mediators. Actor effects describe the influence that one's standing on independent or mediating variables (e.g., the trans woman's communication) has on one's own dependent variables (e.g., self CR-HIV) whereas partner effects describe the influence that one's standing on independent variables has on the dependent variables of one's partner (e.g., the trans woman's effect on her partner's CR-HIV). This technique illuminates the effects that partners in intimate relationships can have on both their own and their partner's behaviors. Actor and partner effects can be evaluated in models with either continuous¹⁰¹ (e.g., problem solving) or categorical dependent variables (e.g., CR-HIV).¹⁰⁰ A closely related approach uses sums and differences of continuous covariates and mediators to quantify within-couple and between-couple effects. For continuous dependent variables, within-couple hypotheses will be tested with a GEE model in which couple-level difference scores on the outcome variable (e.g., communication) will be regressed onto both the couple-level difference and sum scores for the predictor variable (e.g., self-efficacy).¹⁰² Computing sums and differences for categorical outcomes is not feasible, but it is still possible to investigate the effects of sums and differences of individuals' continuous covariates and mediators on individual-level categorical responses (e.g., CR-HIV) to tease apart the separate influences of between-couple and within-couple effects of mediators on individuals' categorical outcomes.

8.14 REFERENCES: List only the 5-10 most relevant references (a separate bibliography can be attached for reference purposes if this study involves novel approaches, agents, or an emerging technology that the IRB may not be familiar with):

2. [name] D, Nemoto T, Iwamoto M, et al. Unprotected sexual behavior and HIV risk in the context of primary partnerships for transgender women. *AIDS Behav.* 2011;15(3):674-682. PMC3049202

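### The exploratory actor-partner analyses treat CR-HIV as an individual outcome, but it is defined only per couple, so own-risk and partner-risk effects cannot be told apart

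*Combined protocol and SAP*

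**What the plan says.** Section 8.11, item 4, sets the unit of the outcome: "CR-HIV (primary outcome) is a couple-level binary indicator of any HIV risk". The coding rule follows that unit. For the value 0: "Couples are coded as 0 if neither partner reports condomless anal or vaginal sex". For the value 1, one or both partners must report condomless sex with a serodiscordant or unknown-status partner; "then the couple is coded as 1 if" the PrEP-adherence or viral-suppression condition also fails. Either partner's behaviour can therefore set the value for both.

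Section 8.13, under the secondary exploratory dyadic analyses, uses the same outcome at another level. It announces: "We will extend the analyses described above to include actor and partner effects for covariates and mediators". An actor effect is described as acting on one's "own dependent variables (e.g., self CR-HIV"), and a partner effect is illustrated by "the trans woman's effect on her partner's CR-HIV". For the sum-and-difference approach, CR-HIV is the example given of "individual-level categorical responses (e.g., CR-HIV"). No section defines a CR-HIV value for a single participant.

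**The concern.** An actor-partner model needs one outcome per person. Its purpose is to ask whether my communication, say, affects my own risk, my partner's risk, or both. A value shared by the two partners contains no information on that distinction. The same holds for separating within-couple from between-couple effects, because the outcome never varies within a couple.

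The output would not look faulty. Software would return two finite coefficients with standard errors, and their equality could be read as mutual influence between partners when it comes only from entering one outcome twice. The difference term would appear as a precise null.

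**Working it through.** The plan gives no figure for these analyses, so there is none to reproduce. The check is algebra, followed by a simulation whose settings are assumptions.

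**Inputs from the protocol.** CR-HIV takes one value per couple per assessment (8.11, item 4). There are 54 couples (8.3) and four follow-up visits (8.9). At least one partner is a trans woman (11.7), so both may be, in which case gender does not distinguish the two members.

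**Pooled model.** Write logit P(Y_i = 1) = b0 + a·X_i + p·X_j, where X_i is one's own predictor and X_j the partner's. If both members carry the couple's Y, each couple contributes the rows (Y, X_1, X_2) and (Y, X_2, X_1). Exchanging the two predictor columns gives back the same data set. So if (a, p) solves the estimating equations, (p, a) does too, and a unique solution must have a = p. This requires both members' rows to be present, and other covariates to be couple-level or entered as own/partner pairs.

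**Sum and difference form.** Because a·X_i + p·X_j = [(a + p)/2]·(X_i + X_j) + [(a − p)/2]·(X_i − X_j), a = p makes the difference coefficient exactly 0.

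**Role-specific models.** The trans woman's equation and her partner's equation have the same Y and the same two predictors, so they are the same regression. The coefficient on her predictor is called her actor effect in one and her partner effect in the other, but it is one number.

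**Simulation.** Assumed: individual actor effect 0.8, partner effect 0.2, intercept −0.8, predictor correlation 0.3, four visits, and a couple value of 1 if either member is at risk. Logistic GEE clustered on couple, pooled model:

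| Couples | Outcome | Actor | Partner | Difference coefficient |
|---|---|---|---|---|
| 54 | couple value copied to both | 0.5474 | 0.5474 | 0.0000 |
| 54 | one value per member | 0.7392 | 0.3389 | (0.7392 − 0.3389)/2 = 0.2002 |
| 43 (54 × 0.8 = 43.2) | couple value copied to both | 0.5024 | 0.5024 | 0.0000 |
| 43 | one value per member | 0.8623 | 0.2403 | (0.8623 − 0.2403)/2 = 0.3110 |
| 5000 | couple value copied to both | 0.5961 | 0.5961 | 0.0000 |
| 5000 | one value per member | 0.7810 | 0.1901 | (0.7810 − 0.1901)/2 = 0.2955 |

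Independence and exchangeable working correlations both gave equal actor and partner coefficients for the copied outcome. Over 200 simulated trials of 54 couples, the largest gap between them was about 1e-15. With one outcome per member the mean gap was 0.58, against the assumed 0.8 − 0.2 = 0.6. The standard error of the zero difference coefficient was about 4e-18, which is zero up to rounding.

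In the role-specific fits for 54 couples with the copied outcome, member 1's actor effect and member 1's effect on member 2 were both 0.7406. Member 2's corresponding pair were both 0.3770.

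**What remains estimable.** Within one role-specific equation the two members' coefficients are free to differ (0.7406 against 0.3770 above). In further simulations of 54 couples, only the trans woman's predictor affected the couple's outcome (log odds ratios 1.0 and 0; assumed intercept −0.3, predictor correlation 0 or 0.3, one or four visits, 1,000 runs per setting). The role-specific fit ranked her predictor higher in 96 to 100% of runs.

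**The case against.** The strongest reply is that the authors meant an individual version. Section 8.13 speaks of a participant's own CR-HIV and of individual responses, and copying the couple's value to both members is only one way to proceed. That is a fair reading of intent. But the only coding rule in the protocol assigns its values to couples. The nearest individual-style definition, of at-risk sex in 8.11, leaves out PrEP adherence and viral suppression and is not called CR-HIV. An analyst would have to choose a definition that the plan does not contain.

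A reader might infer that nothing about the two partners' roles can be learned from CR-HIV. The documents do not support that. The illustrations in 8.13 are role-specific, and such models can still estimate whose predictor relates more strongly to the couple's risk. The loss is confined to separating own risk from the partner's risk, and to the within-couple effect. For couples in which both partners are trans women, gender does not supply the roles and the pooled symmetry applies directly.

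A reader might also infer that the primary test fails, because the primary model is described as having "3-level clustering of observations within participants and participants within dyads". That wording shows a similar mismatch of unit. But the primary comparison is between arms, assigned per couple, and uses no actor or partner coefficient. Nothing here shows that it is affected.

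It is also true that the section is labelled exploratory, that CR-HIV is only one example of an outcome in it, and that none of the listed aims depends on actor-partner effects. This limits the importance of the point without removing the contradiction.

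**Conclusion.** The point holds, within limits. Taken together, the definition in 8.11 and the dyadic analyses in 8.13 specify an analysis that cannot answer its own question for CR-HIV. Pooled actor and partner coefficients are equal by construction, the within-couple effect is not estimable, and each person's role-specific actor and partner effects are one quantity printed twice. A larger sample does not help: the equality is as exact at 5000 couples as at 54.

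The conclusion assumes that the outcome as defined is used for both members. Incomplete pairs, or covariates entered for one member only, could make the printed coefficients differ, but the outcome would still be shared and the difference would not measure own versus partner risk. The simulated values depend on the assumed settings; the equality does not. Continuous individual outcomes in the same section, such as communication or problem solving, are unaffected. The change should be made before analysis, but it concerns exploratory results only.

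**What to change.** For the CR-HIV actor-partner and sum/difference models only, define in section 8.13 a separately named per-participant risk indicator. Build it from that participant's own reported condomless sex with a serodiscordant or unknown-status partner, combined with that participant's own PrEP adherence (if HIV-negative) or viral suppression (if HIV-positive).

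Alternatively, for these analyses, model couple-level CR-HIV with one record per couple per visit on both members' predictors, and drop the actor/partner and within-couple wording for that outcome. This answers whose predictor matters more and needs no new variable, but it gives up the own-versus-partner question.

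The first option costs one derived variable and a change of wording, with no new data collection, since each partner completes a separate survey. It has one limitation to state in the plan. Dried blood spots for PrEP adherence are collected only at in-person visits, hair analysis has been dropped (9.1), and the remote-visit procedures in 8.9 list no PrEP specimen. For some remote visits the indicator will therefore rest on self-report or be missing, and the plan should say which.

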9.0 Biospecimen Collection and/or Bank Administration

9.1 * TYPE OF SPECIMENS (check all that apply): (REQUIRED)

- Blood (provide amount below)
- Tissue (describe below)
- Other type of biospecimen, such as sputum, cerebrospinal fluid, buccal swabs, etc. (describe below)
- Existing/archival materials (name source below)

Briefly describe the types of biospecimens that will be collected. Provide the amount of blood, if applicable. For leftover/existing/archival material, identify the source:

- Oral swab for HIV-antibody testing conducted at the Eligibility Visit
- Fingerstick blood (3-5 drops) for DBS card to assess PrEP adherence at in-person Enrollment and Follow-up visits when not operating remotely.
- Venous Blood (20 ml) approximately 4 teaspoons for HIV RNA Viral Load at in-person Enrollment and Follow-up visits when not operating remotely.

ONLY FOR REMOTE VISITS: Quest Lab-collected blood sample for HIV RNA Viral Load at remote Enrollment and Follow-up visits (remunerated an additional \$40.00).

This protocol is modified to clarify that hair sample analysis will not be pursued by the investigators due to futility.

9.2 * SPECIMENS ARE: (check all that apply): (REQUIRED)

- Leftover specimens from a clinical diagnostic or therapeutic procedure
- Specimens collected for research purposes only (including extra samples taken during a clinical procedure)
- Other

9.3 * FUTURE SPECIMEN USE: Will any specimens or portions of specimens be retained after the study is over for possible use in future research studies: (REQUIRED)

Yes No

9.5 * SPECIMEN DESTINATION: Indicate where specimens will ultimately be stored: (REQUIRED)

Outside Entities: Indicate where specimens will be sent if they will not remain at UCSF (choose at least one; check all that apply):

- Cooperative group bank
- NIH
- Other university or collaborator
- Industry sponsor
- Other

N/A - all specimens will remain at UCSF

Specify to what institution, cooperative group, or company specimens will be transferred:

1. DBS cards will be analyzed at a specialty lab at the University of Colorado
2. HIV viral loads will be processed by Quest (commercial laboratory)

Internal Storage: If specimens will remain at UCSF, in what kind of facility will they reside (choose at least one; check all that apply):

- UCSF repository/bank being established under this protocol
- Existing UCSF specimen repository/bank with IRB approval
- National cooperative group bank housed at UCSF
- Other location at UCSF (please describe)
- N/A - no specimens will be retained at UCSF facilities

9.6 SPECIMENS SENT OUTSIDE UCSF - IDENTIFIABILITY: Will direct identifiers be associated with specimens or shared with other researchers and/or outside entities:

Yes
 No
 N/A - Specimens will not be shared with others

10.0 Drugs and Devices

10.1 * DRUGS AND/OR BIOLOGICS: Are you **STUDYING any drugs and/or biologics that are either approved or unapproved: (REQUIRED)**

Yes No

Note: This question is frequently answered incorrectly. If any drugs or biologics, approved or unapproved, are being administered under this protocol, you should check 'Yes' unless you are absolutely sure that NONE of the drugs are part of the research protocol. Tip: Ask the PI or the sponsor if you are not sure how to answer this question.

10.3 * MEDICAL DEVICES: Are you **STUDYING any medical devices, in vitro diagnostics, or assays that are either approved or unapproved: (REQUIRED)**

Yes No

11.0 Sample Size and Eligibility Criteria

11.1 ENROLLMENT TARGET: How many people will you enroll:

108

If there are multiple participant groups, indicate how many people will be in each group:

Control condition: 54 participants / 27 dyads

11.3 SAMPLE SIZE JUSTIFICATION: Explain how and why the number of people was chosen. For multi-site studies, this is referring to the number that will be enrolled across all sites:

Power analyses were generated using the two-group repeated proportions module in NCSS PASS 15104 to compute minimum detectable effect sizes for the primary analysis to address Hypothesis 1. Our pilot study found standardized effect sizes ranging from .38 to .42,¹⁶ so we powered our study to detect similarly-sized effects in worst-case scenarios where within-participant clustering of outcomes are substantial. The study will begin with 200 participants from 100 couples evenly assigned to the intervention and control groups. Assuming 20% attrition, data from 160 participants from 80 couples will be available for analysis at all time points. Due to the clustered nature of the dyadic data, observations from participants who belong to the same couple will be correlated. In m-PI [name]'s previous study of 190 TW and their male partners, for instance, the average within-couple correlation of sexual risk measurements was $r=.$ 07. Accordingly, we lowered the effective sample size (ESS) input for the power analyses to be $ESS= N/DEFF$, where DEFF is the design effect or variance inflation attributable to using correlated data. DEFF is computed as $1+(M-1)*r$, where M is the number of participants per dyad (i.e., two). Therefore $DEFF=1+(2-1)*.07=1.07$, so $ESS=160/1.07=149$. Assuming, $\alpha=.05$, power=.80, and $ESS=149$, we computed the minimum detectable odds ratio (OR), proportion difference (pdiff), and standardized proportion difference (h) for the proposed time-averaged comparisons, assuming four post-baseline measurements and a wide range of CR-HIV base rates P_0 for levels of risk for TW and their partners seen in the literature.^{4,5,20} Since the within-subject correlation ρ for repeated measures is unknown, we varied it across a wide range from .20 to .80 (see Table 2). The obtained minimum detectable effect size estimates are similar to or smaller than those detected in our pilot study, suggesting that our study is sufficiently powered to test primary Hypothesis 1.

Original Power Calculations. Originally, our sample size of 100 couples would allow us the statistical power to engage in meaningful comparisons between the two intervention arms. We assumed the 200 participants from 100 couples will be evenly assigned to the intervention arms: 50 couples in intervention and 50 couples in control. Assuming 20% attrition, data from 160 participants (80 couples) would have been available for analysis at all time points (i.e., 3-, 6-, 9, 12-month follow up). Using NCSS PASS, we conducted a series of power calculations to determine the maximum sample size requested to address the primary study aims. We computed the minimum detectable odds ratio (OR), proportion difference (pdiff), and standardized proportion difference (h) across our two study arms for the proposed time-averaged comparisons, assuming four post-baseline measurements and a wide range of base proportions for levels of risk for TW and their partners seen in the literature (i.e., 10%-50%). Since the within-subject correlation ρ for repeated measures is unknown, we varied it across a wide range from .20 to .80. Under these conditions, ORs ranged from 0.17 to 0.56, raw proportion differences ranged from 6.6% to 20.5%, and standardized proportion differences (h) ranged from .27 to .42. **Revised Power Calculations.** We repeated the power analysis approach utilized in our proposal submission. The revised power analysis again assumes $\alpha=0.05$, power=0.80, 4 post-baseline measurements, and baseline reference proportions ranging from 0.10 to 0.50. The within-subject correlation for repeated measures was allowed to vary from 0.20 to 0.80. The N of participants was varied from 100 to 200 to illustrate the potential impact of various sample size reductions on the ranges of minimum detectable effect sizes. Conventional benchmarks for effect size are $h=0.20$ for a small effect size, $h=0.50$ for a medium effect size, and $h=0.80$ for a large effect size. Assuming we reach at least 50% of our goal of recruiting 100 couples, under most circumstances we will still be able to detect a small-to-medium effect size. Even under the least advantageous combination of circumstances (recruiting only 50 couples, baseline reference proportions closer to 10%, and very high correlations between repeated measures), a medium-to-large effect size is still detectable.

Our Data Safety Monitoring Board (DSMB) reviewed and approved this request on February 14, 2022, and our NIMH sponsor approved the request on July 26, 2022.

11.4 * PARTICIPANT AGE RANGE: Eligible age ranges: (REQUIRED)

- 0-6 years
- 7-12 years
- 13-17 years
- 18-64 years
- 65+

11.5 * STUDY POPULATIONS: Data will be collected from or about the following types of people (check all that apply): (REQUIRED)

- Inpatients
- Outpatients
- Family members or caregivers
- Providers
- People who have a condition but who are not being seen as patients
- Healthy volunteers
- Students
- Staff of UCSF or affiliated institutions
- None of the above

11.6 * SPECIAL SUBJECT GROUPS: Check the populations that may be enrolled: (REQUIRED)

- Children / Minors
- Adult subjects unable to consent for themselves
- Adult subjects unable to consent for themselves (emergency setting)
- Subjects with diminished capacity to consent
- Subjects unable to read, speak or understand English
- Pregnant women
- Fetuses
- Neonates
- Prisoners
- Economically or educationally disadvantaged persons
- None of the above

11.7 INCLUSION CRITERIA: Briefly describe the population(s) that will be involved in this study. Include anyone that data will be collected from or about (e.g. patients, healthy controls, caregivers, providers, administrators, students, parents, family members, etc.):

Inclusion criteria:

1. Age 18 or older;
2. Self-reported primary partnership for at least 3 months;
3. Have had sex with primary partner in the last 6 months;
4. Either partner has had condomless sex with any partner in last 6 months;
5. At least one partner must be a trans woman;
6. Able to provide informed consent;
7. English speaking; and
8. Couples may be HIV-negative concordant, HIV-positive concordant, or HIV serodiscordant.

11.8 EXCLUSION CRITERIA: List any exclusion criteria (e.g. reasons why someone would not be included in the study):

Exclusion criteria:

1. Appears to be psychotic, or otherwise unable to complete Informed Consent procedures.
2. Participation would be unsafe.

11.9 * RESEARCH CONDUCTED ON PATIENT CARE WARDS: Do any study activities take place on any patient care units including inpatient wards, peri- or post-operative care units, operating rooms, or in the Emergency Department at UCSF Health medical facilities: (REQUIRED)

Yes No

11.11 * EMERGENCY DEPARTMENT: Does your protocol or study involve any of the following patient related activities in the emergency department (e.g. subject identification, recruitment, consent, blood draws, specimen retrieval, involvement of ED staff (nursing, tech, and/or physician), or any other ED based procedures): (REQUIRED)

Yes No

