Our team recently completed a pilot RCT of CHIP, an HIV prevention program for TW couples. CHIP was adapted from Project Connect, a CDC-endorsed "high impact" HIV intervention for couples that focuses on relationship quality/functioning, communication, and shared commitment. The design of CHIP involved iterative rounds of quantitative and qualitative research with TW-male couples to identify intervention targets and gender-sensitive delivery processes for HIV prevention for racially/ethnically diverse TW-male partners across different age groups. Over a 13-month outreach and recruitment period, the study team recruited 56 TW-male partners (n=112 participants) and examined the acceptability, feasibility, and 3-month outcomes on sexual risk behavior (45.5 % Black, 14.3 % Hispanic, 24.1 Other, and 16.1 % White). Couples randomized to the control arm received basic HIV information. Couples in the intervention arm (CHIP) received three sessions designed to improve relationship and couples' communication skills to promote HIV risk reduction. They received two couples-focused sessions in which the couple met with a counselor to promote positive relationship dynamics, communication skills, and to identify HIV risk reduction goals; each partner also had 1 individual session with the counselor to describe their personal HIV prevention concerns in the context of their relationship and with outside partners. At 3-month followup, participants in the intervention arm had lower odds of CAS with primary partners (OR=0.5, 95%CI: 0.3-1.0), reduced odds of engaging in sex with any casual partner (OR=0.3, 95%CI: 0.1-1.0), and reductions in overall number of casual partners (B=-1.45, SE=0.4) compared with the control arm. In exit interviews, TW and male intervention participants commented favorably on focusing on strengthening relationships, communication around HIV, and coping with gender minority stressors, and described interest in further couples-focused programs with more than three sessions. These results provide support for the feasibility and acceptability of CHIP, and demonstrate the team's ability to recruit and implement a couples-focused intervention for TW and their primary partners.

8.6 * TREATMENT PROTOCOL: Is this a treatment study, i.e. does this study intend to provide treatment to individuals with a medical or psychological condition: (REQUIRED)

Yes No

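### Section 11.3 still claims detectable effects no larger than the pilot's and adequate power; that was worked out for 100 couples and fails in most of the grid at the 54 now enrolled

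*Combined protocol and SAP*

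**What the plan says.** The sample size justification in section 11.3 of the combined protocol and SAP opens from the pilot: "Our pilot study found standardized effect sizes ranging from .38 to .42". It does not name the metric or the outcome. It says the study was powered for effects of that size even when repeated measures within a participant are strongly correlated. It then takes 200 participants in 100 couples, 20% attrition and a design effect of 1.07 to reach an effective sample size (ESS) of 149. It concludes that "The obtained minimum detectable effect size estimates are similar to or smaller than those detected in our pilot study" and that the primary hypothesis is therefore adequately powered.

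The Original Power Calculations paragraph gives the results for 100 couples: "ORs ranged from 0.17 to 0.56, raw proportion differences ranged from 6.6% to 20.5" per cent, with h from .27 to .42. The Revised Power Calculations paragraph assumes "power=0.80, 4 post-baseline measurements, and baseline reference proportions ranging from 0.10 to 0.50" and lets the number of participants vary from 100 to 200. It reports the outcome only in effect-size adjectives. It treats "baseline reference proportions closer to 10" per cent, with very high correlation and 50 couples, as the least favourable case.

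The pilot effects appear in section 8.5 as "lower odds of CAS with primary partners (OR=0.5, 95%CI: 0.3-1.0", as OR 0.3 (95% CI 0.1 to 1.0) for sex with any casual partner, and as a reduction of 1.45 in the number of casual partners. Sections 8.3 and 11.1 set enrolment at 54 couples, 108 participants.

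**The concern.** The sentence comparing detectable effects with the pilot is the only place in section 11.3 that ties the sample size to an expected effect. It stands in the present tense under an enrolment target of 108, but its figures belong to a design almost twice as large. The revised paragraph gives no detectable odds ratio or risk difference for 54 couples and does not repeat the pilot comparison. A reader would take the pilot-based assurance to cover the trial being run. If the result is null, that assurance invites the conclusion that an effect of the pilot's size has been ruled out.

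A second question is whether the comparison uses one scale. The detectable effects are Cohen's h, the pilot range has no named metric, and section 8.5 reports the binary pilot effects only as odds ratios.

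**Working it through.** **Inputs.** Alpha: "will be set at .05 for this planned comparison" (section 8.13). Sidedness is not stated; two-sided is assumed because it reproduces the plan's ranges and one-sided does not (one-sided gives OR 0.21 to 0.60 and h .25 to .37). Power .80, four post-baseline measures and base rates P0 of .10 to .50 are from section 11.3. For the within-participant correlation rho, "we varied it across a wide range from .20 to .80". The plan's table of detectable effects is not in the text available, so I used P0 = .1, .2, .3, .4, .5 by rho = .2, .5, .8, which makes 15 cells.

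**Formula.** Effective observations per arm: n = (ESS/2) x 4/(1 + 3 rho). The detectable OR solves |ln OR| = (1.960 + 0.842) x sqrt(2/(pbar(1 - pbar) n)), where pbar is the mean of P0 and the intervention-arm proportion. Power for a given OR is Phi(|ln OR|/SE - 1.960), with SE the square-root term. h = 2 arcsin(sqrt P0) - 2 arcsin(sqrt P1).

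**Reproducing the plan, 100 couples.** ESS = 160/1.07 = 149. The grid gives OR 0.166 to 0.556, difference 6.6% to 20.4% and h .275 to .419. The plan states 0.17 to 0.56, 6.6% to 20.5% and .27 to .42, so the method matches within rounding.

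**54 couples, same allowances.** 108 x 0.80 = 86.4; 86.4/1.07 = 80.7. Entries are for rho .2 / .5 / .8.

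| P0 | Detectable OR | Detectable h | Power, OR 0.5 (%) | Power, OR 0.3 (%) |
|---|---|---|---|---|
| .1 | .19 / .12 / .08 | .354 / .415 / .456 | 26 / 18 / 14 | 57 / 40 / 31 |
| .2 | .32 / .23 / .17 | .378 / .459 / .519 | 43 / 30 / 23 | 83 / 65 / 52 |
| .3 | .39 / .30 / .24 | .386 / .475 / .545 | 55 / 39 / 30 | 93 / 79 / 66 |
| .4 | .43 / .34 / .28 | .390 / .483 / .558 | 63 / 45 / 35 | 97 / 87 / 75 |
| .5 | .45 / .36 / .30 | .391 / .487 / .564 | 68 / 49 / 38 | 98 / 91 / 81 |

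Example, P0 = .5 and rho = .2: n = 40.37 x 4/1.6 = 100.9. OR 0.5 gives P1 = .333 and pbar = .417, so SE = sqrt(2/(.2431 x 100.9)) = .286. Then .693/.286 - 1.960 = .467, which is power of 68%.

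Nine of 15 cells have h above .42.

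**Cells with at least 80% power for each pilot odds ratio.**

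| | 100 couples (ESS 149) | 54 couples (ESS 80.7) |
|---|---|---|
| OR 0.5 | 3 of 15 (power 23% to 91%) | 0 of 15 (14% to 68%) |
| OR 0.3 | 12 of 15 | 7 of 15 |

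The three cells for OR 0.5 at 100 couples all have rho = .2 and P0 of .3 or more. At rho = .8, the strong-correlation case the plan says it allowed for, power for OR 0.5 at 100 couples is 23% to 62%. At 54 couples with no attrition (108/1.07 = 100.9) OR 0.5 still reaches 80% in no cell, with a best power of about 77%. Only with neither attrition nor design effect (N = 108) does one corner, P0 = .5 and rho = .2, just reach OR 0.501.

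**Scale of .38 to .42.** The two usual log-odds-to-d conversions of OR 0.5 are ln 2 x sqrt(3)/pi = .382 and ln 2/1.65 = .420, which match both ends of the range. As h, OR 0.5 is .18 at P0 = .1, .34 at P0 = .5 and at most about .345 at any base rate. OR 0.3 at P0 = .2 gives h of about .39.

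**The case against.** The best defence is that the sentence belongs to the 100-couple calculation, which the plan itself labels original and follows with a revised paragraph that claims nothing about the pilot. That is fair as history. But the sentence has not been withdrawn or marked as superseded, and the revised paragraph puts no figures in its place.

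Several stronger readings are tempting, and the documents do not support them.

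- A reader might infer that the claim was already false at 100 couples. That holds only against OR 0.5. Against OR 0.3 it is largely true (12 of 15 cells). At face value, h of .27 to .42 set beside .38 to .42 also fits the sentence.
- A reader might infer that a scale error is proved. The match to d conversions of OR 0.5 is close, and .38 to .42 cannot be the h of that odds ratio. But the metric is not stated, and an h derived from OR 0.3 is not excluded.
- A reader might infer from the stated OR range of 0.17 to 0.56 alone that nearly all scenarios need more than OR 0.5. Two endpoints do not show how the scenarios are distributed.
- A reader might call the least-favourable-case sentence wrong. On the OR scale a 10% base rate is the worst case. It is not on h: at 50 couples and rho = .8, h is .43 to .47 at 10% and .51 to .58 at 50% (without and with attrition and design effect). Neither range exceeds the plan's medium-to-large wording. Naming the scale is a clarification only.

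It is also true that OR 0.5 concerns condomless anal sex with the primary partner at 3 months, whereas CR-HIV also depends on PrEP adherence and viral suppression. Neither pilot odds ratio is the expected effect on CR-HIV, which is why both should be reported.

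**Conclusion.** The concern holds for the present design. At 54 couples the plan's own method gives detectable effects of OR 0.08 to 0.45 and h .35 to .56. The statement therefore fails in 9 of 15 cells even on the reading most favourable to it, with .38 to .42 taken as h. Those nine cells run from h of .46 to .56, and a loose reading of similar might cover the lowest of them but not the highest. Power for OR 0.5 never reaches 80%, and for OR 0.3 it does so in 7 of 15 cells. A scale mismatch in the comparison is suggested but not established.

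This rests on two-sided alpha of .05, carrying the plan's 20% attrition and design effect over to 54 couples, and its participant-based effective sample size. The cell counts depend on the grid chosen here. The finding for OR 0.5 at 54 couples survives dropping the attrition allowance.

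**What to change.** In section 11.3:

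1. Delete the sentence comparing detectable effects with the pilot and concluding that power is adequate, or restate it for 54 couples.
2. Tabulate the minimum detectable OR, risk difference and h by base rate and rho for 54 couples, with the attrition and design effect used.
3. Name the metric and the pilot outcome behind .38 to .42.
4. State power at 54 couples for both OR 0.5 and OR 0.3.
5. As a clarification, name the scale on which a 10% base rate is the least favourable case, and give the proportions implied: at 50 couples and rho = .8, a fall from 10% to about 1%.

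The cost is rewording and less favourable stated figures. No extra enrolment and no change to the analysis is needed.
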